7.3 Accountability Procedures for the Study Intervention/Investigational Product(s)

MTBVAC will be shipped from Biofabri to the clinical trial site. The frequency of product distribution and amount of product distributed will depend on the rate of enrollment of study participants. A WHO pre-qualified BCG vaccine will be supplied by the Sponsor from a registered local supplier or imported under the applicable South African Medicines Control Council regulations.

The study vaccine manager is required to maintain accurate investigational product accountability records. Instructions and forms to be completed and kept for accountability will be provided to the study vaccine manager. If the study vaccine manager wishes to use clinical trial site-specific accountability forms, these must be reviewed and approved in advance by Biofabri. Upon completion of the study, all investigational product management records will be copied, and the copies returned to Biofabri or its designee. The originals must be maintained at the clinical trial site with the rest of the study records.

Biofabri must provide authorization for the disposition of any unused investigational product or BCG. Unused investigational product will be destroyed according to the facility's SOPs. Any disposal of investigational product conducted at the clinical trial site must be documented in the study file.

7.4 Assessment of Participant Compliance with Study Intervention/Investigational Product

The vaccines will be administered at the Vaccination clinic, SATVI, under the supervision of investigators or nurses trained in the management of anaphylactic reactions.

7.5 Concomitant Medications/Treatments

The collection of information on concomitant medications used by participants following vaccination will coincide with the collection period of adverse events (see Section 10.1). In addition, information on all concomitant medications associated with the treatment of adverse events and serious adverse events will be collected throughout the study.

Concomitant medication includes prescription and non-prescription drugs or other treatments, and any vaccines other than the investigational product. The name of the medication, treatment start and stop dates (or 'ongoing'), and indication must be recorded on the Concomitant Medications electronic case report form (eCRF). The indication recorded on the Concomitant Medications eCRF must correspond to a medical term/diagnosis recorded on the Adverse Event (AE) eCRF, or to a pre-existing condition noted in the participant's medical history, or be noted as prophylaxis, e.g., dietary supplement or routine vaccinations.

8 STUDY SCHEDULE

A Schedule of Events depicting all visit-specific procedures is provided in Appendix A, including the acceptable time windows. Detailed descriptions of procedures to be carried out at each visit are presented in Sections 0 through 8.6.

All participants who are assigned a participant identification number and receive investigational product will be followed according to the protocol unless consent is withdrawn.

Participants will be instructed to contact a study team member to report new signs and symptoms or new or worsening adverse events and will be referred for medical attention as applicable.

During each clinic visit, participants will be reminded to notify a study team member of the following:

- The occurrence of AEs and SAEs during the respective reporting periods.
- Receipt of any concomitant medications during the applicable reporting period.
- Plans to move or if contact information changes.
- If participant has decided to withdraw from the study.
- Change in general health status.
- Any other change in status that may affect the participant's participation (e.g. plan to participate in another investigational study).

If the clinical trial site's study team members are unable to establish contact with a participant who misses a scheduled study visit, the clinical trial site must make every possible effort to reestablish contact and document such efforts. If contact is re-established, then the participant will resume participation in the study. If contact with the participant cannot be re-established by the participant's calculated Study Day 365 visit date, then a determination of "lost to follow-up" should be made on the date of the last attended study visit.

Upon completion of the study, participants will be provided a letter and a card that briefly describe their participation in the study.

8.1 Screening

Written informed consent must be obtained before any screening procedures are performed.

Pregnant women will be approached during the third trimester of their pregnancy at the time of their antenatal visits to the state public healthcare clinics. Information on the trial will be presented to them, and if interested, they will be invited to undergo an informed consent session in their language of choice and asked to sign an Informed Consent Form (ICF). Informed consent sessions will be conducted in a private space conducive to confidential discussion, at the clinic, at the participant's home, or at the SATVI site. Where feasible, at least 1 further antenatal contact will be made by the study team with the mother-to-be to remind her of the study procedures and to obtain background information about the mother

and her pregnancy. Clinic and antenatal clinic cards will be marked with an easily identifiable sticker or marking to enable the birthing unit staff to identify potential study participants.

All women are offered HIV testing per standard of care at the antenatal clinics. After signing the ICF, study staff will request access to the HIV result as recorded in the clinic notes, as well as other relevant medical history from medical records. If the pregnant woman has declined to be tested or if the result is unavailable, or if the result is positive, her newborn will not be enrolled into the study. Counseling and treatment of HIV positive mothers will be provided per standard of care by the state healthcare system according to national guidelines. The ICF also includes as separate documents permission to photograph abnormal injection site reactions and to perform investigations for TB when considered necessary by an investigator.

When women who have consented present in labour to the birthing unit, the study team will be notified by the mother-to-be on a dedicated SATVI telephone number provided to her antenatally, as well as by the birthing unit staff when they identify her newborn child as a study participant from information on her antenatal record. After delivery, a study research nurse will go to the birthing unit in person and will confirm with the woman that she still wishes to enroll her child into the trial and will apply the inclusion and exclusion criteria and ensure that routine BCG administration by the clinic staff is postponed. The mother will be given a date when she should attend the clinic for the study day 0 visit. If the mother's discharge from the birthing unit is delayed beyond 96 hours the infant will not be eligible for the study.

Screening procedures

Maternal:

Written informed consent

Assign study participant identification (PID) number

Medical history

Confirm HIV status (mother to be tested if result is not available or if the test was not done within 30 days prior to delivery)

History of active TB or household TB contact

Infant:

On Road to Health Card: confirm no BCG given at birthing unit, confirm birth weight, gestational age and Apgar score meet eligibility criteria.

8.2 Enrollment/Baseline

Study Day 0 (within 96 hours of birth)

Pre-vaccination:

- 1. Verbally reconfirm maternal consent.
- Confirm absence of acute illness in infant.
- 3. Medical history and update of concomitant medication.
- 4. Screening for potential new TB exposure and TB symptoms.
- 5. Vital signs:

- Heart rate, respiratory rate, weight, recumbent length.
- Axillary temperature: must be <38°C.
- 6. History and physical examination by investigator.
- 7. Confirm eligibility for study entry and vaccination.
- 8. Complete Vaccine Request Form, send to study vaccine manager (study pharmacist) who will randomise participant into a study arm according to the next available treatment number in the final randomisation schedule, and then prepare study vaccine.

Vaccination (by Vaccination Nurse):

- 1. Inspect syringe and vaccine volume, confirm PID number, date and time of dose preparation.
- 2. Administer study vaccine intradermally into left deltoid area of the infant's arm. Record date and time of vaccination, presence of a bleb. Apply Opsite plaster.

Post-vaccination:

- 1. Monitor participant for acute adverse events for at least 60 minutes after vaccination.
- 2. Obtain 60±10 minutes post-immunization vital signs (pulse, axillary temperature).
- 3. Examine site of injection 60±10 minutes post-immunization (includes measurement of redness, swelling, and ulceration); replace Opsite plaster.
- 4. Record any adverse events, including systemic solicited adverse events, unsolicited adverse events, solicited and unsolicited injection site reactions, and serious adverse events (including concomitant medications).
- 5. Distribute and review diary card and diary card instructions with participant; review injection site care instructions and distribute Opsite plasters and plastic Ziploc bags.

8.3 Follow-up

Study Day 7

Allowable window for clinic visit is 7±3 days from Study Day 0 visit date.

- 1. Verbally reconfirm consent.
- 2. Update medical history including use of medications.
- 3. Screening for potential new TB exposure and TB symptoms.
- 4. Record feeding practice.
- 5. Vital signs (heart rate, respiratory rate, axillary temperature, weight and recumbent length).
- 6. Focused physical examination.
- 7. Collect and review solicited AE and medication diary card entries for completeness and accuracy. Redistribute AE and medication diary card.
- 8. Record any adverse events, including systemic solicited adverse events, unsolicited adverse events, solicited and unsolicited injection site reactions, and serious adverse events (including concomitant medications).
- 9. Examine site of injection (includes measurement of redness, swelling, and ulceration) and take a pus swab if discharge present.

10. Blood collection for:

- Serum chemistry: includes AST, ALT, GGT, total bilirubin, creatinine.
- Hematology: includes full blood count with differential, and platelet count.

Study Day 28

Allowable window for clinic visit is 28±3 days from Study Day 0 visit date.

- 1. Verbally reconfirm consent.
- 2. Update medical history including use of medications.
- 3. Screening for potential new TB exposure and TB symptoms.
- 4. Record feeding practice.
- 5. Vital signs (heart rate, respiratory rate, axillary temperature, weight and recumbent length).
- 6. Focused physical examination.
- 7. Collect and review solicited AE and medication diary card entries for completeness and accuracy.
- 8. Record any adverse events, including systemic solicited adverse events, unsolicited adverse events, solicited and unsolicited injection site reactions, and serious adverse events (including concomitant medications).
- 9. Examine site of injection (includes measurement of redness, swelling, and ulceration) and take a pus swab if discharge present.
- 10. Blood collection for:
 - Immunogenicity WB-ICS

Study Day 56

Allowable window for clinic visit is 56±7 days from Study Day 0 visit date.

- 1. Verbally reconfirm consent.
- 2. Update medical history including use of medications.
- 3. Screening for potential new TB exposure and TB symptoms.
- 4. Record feeding practice.
- 5. Vital signs (heart rate, respiratory rate, axillary temperature, weight and recumbent length).
- 6. Focused physical examination.
- Record any adverse events, including unsolicited adverse events, solicited and unsolicited injection site reactions, and serious adverse events (including concomitant medications).
- 8. Examine site of injection (includes measurement of redness, swelling, and ulceration) and take a pus swab if discharge present.
- 9. Blood collection for:
 - Immunogenicity WB-ICS
 - QuantiFERON®-TB Gold Plus test

Study Day 120 ±7 days and Study Day 270 ±7 days

Home / telephonic visit if infant tested QFT positive at D56 to enquire about TB signs and symptoms and general well-being

Study Day 182

Allowable window for clinic visit is 182 ±14 days from Study Day 0 visit date.

- 1. Verbally reconfirm consent.
- 2. Update medical history including use of medications.
- 3. Screening for potential new TB exposure and TB symptoms.
- 4. Record feeding practice.
- 5. Vital signs (heart rate, respiratory rate, axillary temperature, weight and recumbent length).
- 6. Focused physical examination.
- 7. Record any adverse events, including unsolicited adverse events and serious adverse events (including concomitant medications).
- 8. Examine site of injection (includes measurement of redness, swelling, and ulceration) and take a pus swab if discharge present.
- 9. Blood collection for:
 - Immunogenicity WB-ICS
 - QuantiFERON®-TB Gold Plus

Partial Cohort Unblinding of Data Post Study Day 182

Once the last Cohort 3 Study D182 visit has been completed, an independent biostatistician be unblinded to available study data. At this point Cohort 1 and Cohort 2 participants will have completed all study visits and these participants and clinical team will be unblinded post Study D365 visit. All available safety data for all cohorts up to the last Cohort 3 Study D182 visit completion; and immunogenicity data for all cohorts up to each cohort's Study D182 visit, will be analysed by the independent, unblinded biostatistician and provided to DSMB for review to determine MTBVAC dose selection for the Phase III study. The Sponsor will review blinded data only in order to keep the blind until post Study D365 visit. The DSMB will be provided with the same blinded data along with unblinding vaccine recipient lists. The DSMB review will allow for a blinded recommendation and input into the dose selection for the Phase III study. For all cohorts, unblinding of the clinical team and participants will take place post Study D365 visit.

Note: The immunology team will remain blinded until immunology database lock.

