skin test (TST) conversion. Three of 8 (37,5%), six of 8 (75%) and 7 of 9 (77,8%) infants who received MTBVAC at 2.5 x 10³, 2.5 x 10⁴ and 2.5 x 10⁵ dose respectively, demonstrated a positive QuantiFERON (QFT) test 180 days after MTBVAC administration, in the absence of known exposure to TB, compared to none of seven BCG recipients. At one year of age none of 8 (0%), two of 8 (25%) and 4 of 9 (44%) infants who received MTBVAC at 2.5 x 10³, 2.5 x 10⁴ and 2.5 x 10⁵ dose respectively, demonstrated a positive QFT result. This new data offers a strong indication of the immunogenicity of MTBVAC in newborns, which requires confirmation in a larger study. Further, since QFT conversion is used as a tool to diagnose *M. tuberculosis* infection in adults and older children, and as an endpoint in exploratory prevention of *M. tuberculosis* infection (POI) vaccine trials, it is critical that the mechanism of MTBVAC-induced QFT conversion and reversion is fully explored. If MTBVAC is shown to be efficacious against TB disease, these data will be important for development of alternative interferongamma release assays (IGRA) for *M. tuberculosis* infection that are not cross-reactive with MTBVAC.

Biofabri, industrial manufacturer and exclusive licensee of MTBVAC, together with intellectual property owner Unizar, has set two independent clinical development pathways for MTBVAC. One pathway focuses on development of MTBVAC for prevention of TB disease in previously BCG vaccinated adults. This clinical trial is based on the clinical development pathway of MTBVAC as a preventive pediatric vaccine that could potentially replace newborn BCG vaccination. A Phase 2a dose-defining study is a pre-requisite for selecting optimal dose for future efficacy trials of MTBVAC in newborns in TB endemic countries.

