Based on observed rates of QFT positivity 1 year after MTBVAC vaccination in infants, half or more of infants who receive MTBVAC may remain QFT positive at end of study and longer. However, it will not be possible to differentiate MTBVAC-induced QFT conversion from QFT conversion as a consequence of natural *M. tuberculosis* infection. Therefore, risk of natural *M. tuberculosis* infection will be minimized by exclusion of infants with known TB exposure, including prior maternal or family history. Infants who demonstrate QFT conversion soon after

MTBVAC administration are more likely to have converted due to vaccine effect than infants who demonstrate QFT conversion later during follow-up, who are more likely to have converted due to natural *M. tuberculosis* infection. Early (D56) post-vaccination QFT conversion in infants with low risk of natural *M. tuberculosis* exposure is assumed to be vaccine-induced and will not be treated with isoniazid preventive therapy (IPT). Infants who demonstrate early QFT conversion at D56 will undergo enhanced screening for potential new TB exposure and TB symptoms during all scheduled study visits, and in addition, during interval telephonic contacts at D120 and D270. QFT samples will be collected at D182 and D365 from infants who tested QFT positive at D56, and stored for later analysis, but since a positive QFT result would not be interpretable, these data will not be used for clinical decision-making. All infants who received MTBVAC and tested QFT positive will receive a card at the end of study indicating that they have received an experimental vaccine that may interfere with interpretation of future IGRA and TST tests for TB infection.

QFT assays will be repeated at D182 and D365 in infants who tested QFT negative at D56. These results will be made available for clinical decision-making. Infants with new QFT conversion events at D182 or D365, and any infant with a reported new household TB contact regardless of QFT status, will be referred to the public health services for IPT since these infants would potentially benefit from TB prophylaxis against *M. tuberculosis* infection as per SA national guidelines, provided that signs and symptoms of active TB disease are absent.

Known Potential Benefits

All infant participants will benefit from enhanced TB screening and facilitated referral and improved access to healthcare providers.

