6.3.2 Masking Procedures

MTBVAC and BCG vaccine will be prepared, and allocation concealed by the site pharmacist. All other site staff will be blinded to vaccine allocation, throughout the follow-up period. Individually-sealed code break envelopes will be held by the pharmacist in case emergency unblinding is necessary.

Data pertaining to the MTBVAC vaccine and to BCG control will be collected in an observer-blinded manner. By observer blinded, we mean that during the course of the study the vaccine recipient and those responsible for the evaluation of safety and reactogenicity study parameters, will all be unaware of which vaccine preparation was administered to a particular participant. To do so, the MTBVAC vaccine and BCG control will be prepared and blinded by the pharmacist, whereas, the vaccination will be administered by the Vaccination Nurse, a research nurse not involved in follow up and safety evaluations of participants. The principal investigator and the sub-investigators will be responsible for assessing safety and reactogenicity. Blinding will be maintained throughout the vaccination and follow-up portions of the vaccine trial. It is not yet known whether MTBVAC offers equivalent or better protection against TB compared to BCG. Therefore, measures to minimize risk of TB will be put in place

throughout the study and, after completion of all Study D365 visits in each cohort and unblinding of the clinical team, 'catch up' BCG vaccination will be given to all MTBVAC vaccinated infants once the last participant of each cohort performed the Post D365 visit.

No set of individual codes will be held at Biofabri's Headquarters. Biofabri's Headquarters will be able to access the individual randomization code from the SATVI Pharmacy randomization register. The code will be broken by the SATVI Pharmacist (Study Contact for Emergency Code Break) only in the case of medical events that the investigator/physician in charge of the participant feels cannot be treated without knowing the identity of the study vaccine(s).

Biofabri's policy (incorporating ICH E2A guidance, EU Clinical Trial Directive) is to unblind any serious adverse event (SAE) report associated with the use of the investigational product, which is unexpected and attributable/suspected, prior to regulatory reporting. The SATVI Pharmacist is responsible for unblinding the treatment assignment in accordance with specified time frames for expedited reporting of SAEs (Refer to Section 10.9).

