10.1 Specification of Safety Parameters

Safety parameters that constitute the primary outcome measures of the study are described in Section 4.2.1. The time periods for collection of adverse events are as follows.

Unsolicited Adverse Events

Unsolicited adverse events will be collected from informed consent until trial completion.

Solicited Adverse Events

Solicited systemic adverse events will be collected post-vaccination through the Study Day 28 visit (with diary cards to be used for 7 days after vaccination).

Solicited injection site reactions will be collected post-vaccination through the Study Day 56 visit (with diary cards to be used for 28 days after vaccination).

Solicited adverse events are events the participant is specifically asked about. These adverse events are commonly observed soon after receipt of vaccines. For this study, solicited adverse events to be collected include:

- Solicited systemic adverse events:
 - fever, irritability, vomiting, diarrhea, drowsiness, poor feeding, skin rash.
- Solicited injection site reaction adverse events:
 - pain, redness, swelling, ulceration, drainage, and regional lymphadenopathy.

Solicited adverse events of injection site reactions will be considered causally related to investigational product.

All participants' caregivers will be provided a diary card to record axillary temperature and information regarding occurrences of these specific events for the first 7 days (for systemic adverse events) or 28 days (for injection site reaction adverse events) of the solicited adverse event reporting period.

Serious Adverse Events

Serious adverse events will be collected throughout the entire study period (i.e., 365 days post-vaccination).

Site of Injection Examination

Site of injection examinations will be performed at the visits noted in the schedule of events in Appendix A. The following will be assessed at each examination:

• Tenderness/pain, redness, swelling, warmth, ulceration, presence of infection/abscess, crusting, drainage, scarring, and regional lymphadenopathy.

Any of the above-mentioned injection site reactions that meet adverse event criteria according to the Toxicity Table in Appendix C will be recorded as adverse events.

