12.4.4 Safety Analyses

12.4.4.1 Adverse Events

The primary endpoint is the frequency of adverse events (AEs) by MTBVAC dose compared to BCG. In order to assess the primary endpoint, analysis of the data will be preceded by a

blinded data review meeting in order to address population determination and miscellaneous data queries pertinent to analysis of the primary endpoint.

Safety and reactogenicity data will be evaluated by study arm and cohort in all participants in the safety analysis set. The primary variable for evaluation of safety will be the frequency of unsolicited, solicited adverse events and injection site reactions at all available post-vaccination time points. The number and percentage of participants with adverse events will be summarized by MedDRA system organ class (SOC) and preferred term (PT), as well as by severity and relationship to study vaccine. Informal between-group comparisons will be performed using the Chi-square or Fisher Exact test. The Cochran-Mantel-Haenzel test will be used to compare the effect of dose on reactogenicity (injection site adverse events).

Separate listings will be provided for participants with serious adverse events. SAEs may also be summarized by MedDRA system organ class and preferred term.

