APPENDIX A. SCHEDULE OF EVENTS

		Study day Visit Window (hrs/days)							
Evaluation	Screen	D0	D7	D28	D56	D182	D365	Post D365	Early termination
	NA	+96 hrs	±3d	±3d	±7d	±14d	±14d	NA	NA
Informed consent process	Ma								
Medical history	М								
TB symptoms or household TB contact	М	х	Х	х	х	х	х	х	х
Maternal HIV result available	М								
Verbally reconfirm consent	М	М	М	М	М	M	М	М	
Verify eligibility criteria	Х	Х							
Vital signs, length, weight		Х	Х	х	х	х	Х	Х	X
Record feeding practice		Х	Х	Х	Х	х	х	х	х
Physical examination		Х	Х	Х	Х	х	х	х	х
Recording of concomitant medication		Х	Х	х	Х	х	х	х	х
Randomization		Х							
MTBVAC/BCG administration		Х							
Safety blood sampling (mL) ^b			2						
QuantiFERON®-TB Gold Plus (mL)b					4 ^d	4	4		4
Whole blood (mL) ^b				2	2	4	4		
(12-hour WB-ICS)							7		
Distribute/review diary cards		Х	Х						
Solicited systemic adverse events (incl. concomitant medications)		х	x	х					
Unsolicited adverse events (incl. concomitant medications)		х	x	х	х	х	х		х
Solicited and unsolicited injection site reaction adverse events (incl. concomitant medications)		х	х	х	х				
Serious adverse events (incl. concomitant medications)		х	х	х	х	х	x		x
Site of injection examination swab if discharge		х	Х	х	х	х	х		x
Rescue dose BCG post unblinding of cohort ^c								x	
Approximate per visit phlebotomy volume (mL) ^a			2	2	6	8	8		4
Cumulative phlebotomy volume (mL)b			2	4	10	18	26		NA

^a Maternal - the mother signs once, antenatally, and thereafter reconfirms consent orally at each visit

^b Acceptable infant blood sample volumes in clinical research are limited to <3% of the total blood volume (TBV), and no more than 3mL/kg over an 8 week period

^c Telephonic contact/ home visit approximately 14 days post BCG to confirm infant's wellbeing incl. BCG injection site reaction

^d If QFT positive at D56 a home/telephonic visit will be done at D120±7d and 270±7d to monitor infant's wellbeing, specifically enquiring about TB signs and symptoms

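### The D120 and D270 contacts depend on the D56 QFT result, so later unsolicited AEs are sought unequally in MTBVAC and BCG infants, and a positive result points to MTBVAC

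*Combined protocol and SAP*

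**What the plan says.** Section 8.3 schedules the D120 and D270 contacts conditionally: "Home / telephonic visit if infant tested QFT positive at D56 to enquire about TB signs and symptoms and general well-being". Footnote d of Appendix A repeats the condition: "If QFT positive at D56 a home/telephonic visit will be done at D120±7d and 270±7d to monitor infant's wellbeing". No section gives QFT-negative infants a matching contact.

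Sections 3.3.1 and 9.1.1 add a second difference, which also applies at scheduled visits: "Infants who demonstrate early QFT conversion at D56 will undergo enhanced screening for potential new TB exposure and TB symptoms". They make later QFT handling depend on the same result. D182 and D365 results are released for clinical use in infants negative at D56, and stored without clinical use in those positive at D56. Both sections presume that an early positive in a low-exposure infant comes from the vaccine.

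On safety, Section 12.4.4.1 states: "The primary endpoint is the frequency of adverse events (AEs) by MTBVAC dose compared to BCG". Section 10.1 sets the window: "Unsolicited adverse events will be collected from informed consent until trial completion". Solicited systemic events close at D28 and solicited injection-site events at D56.

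On masking, Section 6.3.2 exempts only the pharmacist: "All other site staff will be blinded to vaccine allocation, throughout the follow-up period". The same section makes the investigators responsible for assessing safety, and Section 10.2.1 requires causality to be judged without knowing which vaccine was given.

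Section 3.2 supplies the Phase 1b QFT data at D180. "Three of 8 (37,5%), six of 8 (75%) and 7 of 9 (77,8%) infants" were positive on 2.5 x 10³, 2.5 x 10⁴ and 2.5 x 10⁵ CFU respectively, "in the absence of known exposure to TB, compared to none of seven BCG recipients".

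**The concern.** A comparison of AE frequency between arms assumes that events are looked for equally in each. Here the number of scheduled enquiries after D56 depends on a result that the vaccine itself is expected to produce, so follow-up intensity is linked to arm by design. The calls ask about TB symptoms and general well-being, and anything a caregiver reports falls within the unsolicited AE window. Suspected TB is immediately reportable under Section 10.3.2, so a sensitive outcome is among those sought unequally.

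The data feed a decision. Under Sections 8.3 and 12.3.1, Phase III dose selection uses all safety data available when Cohort 3 completes D182. By then Cohorts 1 and 2 have finished follow-up, so their data include both conditional contacts.

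The second issue is masking. Someone at the site must know the D56 result to arrange the contacts, apply the enhanced screening and decide whose later QFT results are released. No section keeps that result from those who grade severity and causality. Section 15.3 also has mothers told about MTBVAC's effect on these tests and about the two extra calls.

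**Working it through.** **Inputs.** Allocation is 75 MTBVAC and 24 BCG (Section 5). QFT positivity at D180 in Phase 1b comes from Section 3.2. Three assumptions are needed:
- The D180 rates stand in for D56, because no D56 rate is given. Section 3.3.1 postulates conversion by D56 with decline afterwards.
- 2.5 x 10⁶ CFU behaves like 2.5 x 10⁵ CFU, because no infant rate exists for it.
- BCG positivity is varied, because 0 of 7 is a small sample.

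**Step 1: the plan's own figures.** 3/8 = 37.5%, 6/8 = 75.0% and 7/9 = 77.8%; all reproduce. For 0/7 the exact 95% interval is 0 to 41%.

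**Step 2: expected QFT-positive infants.** MTBVAC: 25 × 0.75 + 50 × 0.778 = 18.75 + 38.89 = 57.6 of 75. Under the fallback Cohort 3 split: 37 × 0.75 + 38 × 0.778 = 57.3. BCG: 24 × b, where b is the BCG positivity rate.

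**Step 3: scheduled contacts after D56.** A positive infant has D120, D182, D270 and D365, which is four. A negative infant has D182 and D365, which is two. The mean on MTBVAC is 2 + 2 × 57.6/75 = 3.54. The mean on BCG is 2 + 2b: 2.00 at b = 0, 2.20 at b = 0.10 and 2.82 at b = 0.41.

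**Step 4: what a positive result says about the arm.** P(MTBVAC | positive) = 57.6 / (57.6 + 24b). By allocation alone it is 75/99 = 76%. The last column replaces the MTBVAC rate with 37.5% (28.1 of 75), as a low case.

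| BCG rate b | BCG positives | P(MTBVAC given positive) | Same, MTBVAC rate 37.5% |
|---|---|---|---|
| 0% | 0 | 100% | 100% |
| 5% | 1.2 | 98% | 96% |
| 10% | 2.4 | 96% | 92% |
| 20% | 4.8 | 92% | 85% |
| 41% | 9.8 | 85% | 74% |

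Only when a low MTBVAC rate is paired with the upper limit for BCG does the result stop pointing to MTBVAC.

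**Step 5: what a negative result says.** Negatives are 75 − 57.6 = 17.4 on MTBVAC and, at b = 0, 24 on BCG. P(BCG | negative) = 24/41.4 = 58%, up from 24% by allocation. That leaves the arm near even odds, so a negative result does not identify it.

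**Step 6: which events are exposed.** Solicited systemic events close at D28 and injection-site events at D56, both before D120. What remains is unsolicited AEs, SAEs and suspected TB arising after D56.

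**Step 7: size.** The documents give no detection probabilities, so the bias cannot be calculated. To show only how far it depends on them, suppose equal true risk, 77% of MTBVAC infants contacted, and no extra contacts on BCG. The apparent MTBVAC/BCG ratio is (0.77 × q₄ + 0.23 × q₂)/q₂, where q₄ and q₂ are assumed detection probabilities with four and two contacts:
- q₂ = 0.90, q₄ = 0.95 gives 1.04.
- q₂ = 0.70, q₄ = 0.90 gives 1.22.
- q₂ = 0.50, q₄ = 0.80 gives 1.46.
- If every such event would surface by D365 anyway, q₄ = q₂ and the ratio is 1.00.

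**The case against.** The strongest reply is that little of the primary safety endpoint is exposed. Solicited events close before any extra contact, the dose-effect test named in Section 12.4.4.1 concerns injection-site events, and escalation rests on D28 data. All infants are asked about AEs at D182 and D365, caregivers are told to report symptoms between visits, and outside medical records are sought. Much of the difference may therefore be earlier detection, not extra events. Section 12.4.4.1 counts participants with AEs, so an infant already counted adds nothing to the overall percentage. Section 12.1 rules out formal testing. The contacts also have a stated purpose: TB monitoring of infants whose later QFT results are considered uninterpretable. All of this stands. It limits the scope and leaves the size open, but does not make follow-up equal.

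Several stronger readings are tempting and are not supported:
- **More AEs at the doses that convert most.** Section 3.2 shows 6/8 against 7/9, which cannot be told apart, with no infant rate for 2.5 x 10⁶ CFU. No gradient across this trial's doses is shown.
- **A definite excess of suspected TB on MTBVAC.** An opposite asymmetry exists: later QFT results are released and acted on only for infants negative at D56. The net direction is not established.
- **Assessors are in fact unblinded.** No section says who makes the calls or who sees the D56 result. That AE graders will know it is a reasonable inference, not a stated fact.
- **Excluding AEs first reported at D120 or D270 restores balance.** It would remove MTBVAC events that would have surfaced at D182 or D365 while keeping the same events on BCG. If, as an assumption, 15% of infants in every arm had such an event and 75% of MTBVAC infants were called, exclusion would create a false MTBVAC deficit of 0.75 × 15 = about 11 points.

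**Conclusion.** The point holds with limited scope. Scheduled contact after D56 is four against two according to D56 QFT status, with expected means of about 3.5 on MTBVAC and 2.0–2.2 on BCG at BCG positivity of 0–10%. Ascertainment of unsolicited AEs, SAEs and suspected TB after D56 is therefore unequal between MTBVAC and BCG. Solicited events are unaffected. The size of any resulting bias is unknown, and the harm is to interpretation of an informal comparison, not to an error rate.

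A positive D56 result known to AE graders would point strongly to MTBVAC: 96–100% at BCG positivity of 0–10% and about 85% at 41%, against 76% by allocation. This rests on D180 rates from 8, 9 and 7 infants standing in for D56, and on an assumed rate for 2.5 x 10⁶ CFU. It conflicts with the unqualified blinding statement in Section 6.3.2 and the causality requirement in Section 10.2.1. A reader might infer that universal calls would restore the blind. They would not, because the enhanced screening and the handling of D182 and D365 QFT results would still depend on the D56 result.

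**What to change.** 1. **Equal contact.** Make the D120 and D270 contacts universal, with one script for all infants, and add them to Appendix A with AE recording. All existing TB monitoring stays. The total is 99 × 2 = 198 contacts against 115 expected now (2 × 57.6), so about 83 more; at a flat 75% positivity, 198 − 112.5 = about 86 more. These are short contacts by existing staff.
2. **Traceable ascertainment.** Record on the eCRF the contact at which each AE was first reported. Keep every AE in the primary comparison. Add a sensitivity analysis that shows separately the post-D56 AEs first reported at D120 or D270, without dropping SAEs or suspected TB. The cost is one eCRF field and one SAP sentence. This is worth doing even if the first change is not made.
3. **Honest masking.** Qualify the blinding statement for severity and causality grading after D56, or have grading done without sight of the D56 result where existing roles allow. The first option is a wording change; the second needs a check of who holds the result.
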